Per October 2024, the around 471 children available for the follow-up. At that time, participation of controls and cases at ages the 18 months assessments were 90% and 83%.

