3.2 Design

We have chosen the stepped wedge cluster randomized design (163-165) mainly for two reasons. First, it is more feasible to randomize at the municipality level as compared to the level of the individual child or CHN. An RCTs based on randomization of the individual child or nurse would be associated with more logistical demand on the individual municipality or nurse as compared to the stepped wedge design as they would be having both the intervention and the control condition running simultaneously. For practical reasons, all municipalities cannot be trained at the same time but have to be split into three groups, and with the stepped wedge design we utilize this and randomly allocate the 16 participating municipalities to the time at which their health nurses have been trained and start offering the intervention to families. Also, with the SWD spill over is reduced by the randomization of clusters as compared to individual randomization. Second, in the stepped wedge design, interventions are introduced in a stepwise manner to all participating clusters (municipalities in this case) which encourages participation for those who would otherwise have been randomized to the control condition. Initial feedback from our interactions with the municipalities reveals that their motivation is strongly associated with being able to offer the intervention, as many municipalities prioritize early intervention highly. Also, with the stepped wedge design control families are recruited in the early phases of the trial, which enhances the recruiting of a control group with the level of usual care offered at the beginning of the trial. In the control period no participants receive intervention and sequential random crossover to the intervention cannot be reversed (166).

An important advantage of the stepped wedge design is that families only need to consent to participate in a research study and not to be randomized. In our experience this makes a big difference not only to the families, but also the front personnel who are recruiting the families. With a longer recruitment period and higher expected acceptance rates, the stepped wedge design will

INFANT HEALTH

[figure not shown]

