4.2 Statistical analyses

Statistical analyses will be carried out according to the intention to treat principle, where the participants are analyzed according to their CAU/intervention recruitment group. For continuous outcomes (including the primary outcome measured as the SDQ total difficulties score), linear mixed models will be fitted to compare the control group receiving care as usual (CAU) and the VIPP-PUF intervention group. For binary outcomes (e.g., border line/abnormal versus normal SDQ score), logistic mixed-effects regression models will be fitted to compare the control and intervention groups. All models include municipality-specific random effects, allowing for the correlation between outcomes of children from the same municipality. Likewise, cluster-specific random effects will be included.

Differences in weight-for-length between intervention and control groups will be evaluated using analysis of covariance (ANCOVA). Associations between weight-for-length z-score and selected risk factors based on their associations with infant behavior and preschool obesity in the published literature will be explored using linear regression. To assess differences in parental feeding practice and infant eating behavior between intervention and control groups, mean scores on the feeding and eating questionnaires subscales are calculated and analyzed using linear mixed models for repeated measurements, including participant-specific random effects. Further, exploratory analyses regarding feeding practices, eating behavior, and weight development will be carried out.

Other prognostic factors identified from the literature *á priori* will be included in analyses. Examples include parents’ education, employment status, household income, ethnicity, parental age, parental mental health problems and marital status (all obtained from national registers) (160); at the child level, sex, birth parameters, weight-for-length z-scores from birth to age 9 months, regulatory problems from ages 2-9 months, and ASQ:SE2 score at 9-10 months; and at the

INFANT HEALTH

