municipality level, e.g., level of social disadvantage. Interaction terms will be included to explore possible differences in intervention effect (on the primary outcome SDQ score only) between gender, pre-defined subgroups based on weight-for-length z-scores 0-9 months, low versus high scores of regulatory problems 2-9 months (0-2 problems versus ≥ 3 problems of eating, sleep or emotional dysregulation); low versus high baseline ASQ:SE2 scores and parental characteristics. Also, additional analyses of effect modification will further explore the effect by different population groups (socio-economic position, family structure, and migration status).

We will use path analysis to explore whether the effect of the intervention on weight-for-length z-score at age 18 and 24 months is mediated through the above-mentioned risk factors for childhood overweight. Using path analysis, we can assess the direct effect of the intervention, corresponding to the proportion not mediated through risk factors for child overweight, and the indirect effects of the intervention, corresponding to the proportion mediated through selected risk factors for childhood overweight. The total effect is the sum of the direct and indirect effects.

(Please see the WP4 protocol, WP 4b (Version January 2022) for further details regarding the statistical analyses of the process evaluation).

Sample size re-calculation

Based on recent research (239), an updated sample size calculation has been carried out for testing the primary outcome (the SDQ total score). The mean SDQ total score at the baseline, in children with ≥ 3 problems, is expected to be 13 (182) and the intervention group is now expected to reduce the mean SDQ total score to 11 (179). Consequently, to detect a difference in the SDQ total score of 2 while assuming a standard deviation of 5.7 (239), a small cluster effect (assuming an intraclass correlation of 0.001 as there are only 3 large clusters involved), and a significance level of 0.05 and with 80% power, we need a total sample size of 306 participants (240) (21). We expect a participation rate of 85% at the baseline and a 30% dropout rate by the 24-month follow-up assessment, leaving a total of 460 children available for assessments of the primary outcomes, conditioned a recruitment of about 780 children at baseline.

5 Ethics

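### The 306-participant, 80% power statement and the primary SDQ model both leave out step (period), although the trial is a stepped wedge

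*Protocol*

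**What the plan says.** Section 4.2 of the Protocol, under the sample size re-calculation, takes a difference of 2 SDQ points, an SD of 5.7, a significance level of 0.05 and "a small cluster effect (assuming an intraclass correlation of 0.001 as there are only 3 large clusters involved". It concludes that "with 80% power, we need a total sample size of 306 participants". With 85% participation and 30% dropout from about 780 children, it expects to finish above that number, "leaving a total of 460 children available for assessments of the primary outcomes". The source cited for the calculation is a general text on cluster randomised trials. No step, period or calendar-time adjustment is mentioned.

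On the model, the same section says "All models include municipality-specific random effects, allowing for the correlation between outcomes of children from the same municipality" and adds "Likewise, cluster-specific random effects will be included". Covariates are planned too: "Other prognostic factors identified from the literature" are to be included, with examples such as parental education and the baseline ASQ:SE2. No example is calendar time, and no period term is named.

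Section 3.2 describes a stepped wedge that will "randomly allocate the 16 participating municipalities to the time at which their health nurses have been trained". The municipalities form three groups (6+5+5). All are under usual care in Step 0, and the groups cross over at Steps 1, 2 and 3. The sections on design, model and sample size in the Combined protocol and SAP carry the same text.

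Only the Protocol has the later status note in section 3.1: "Per October 2024, the around 471 children available for the follow-up".

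**The concern.** In a stepped wedge the share of children on intervention rises from none in the first step to all in the last. Any change over time in the mean SDQ, for whatever reason, is then mixed with the intervention effect unless the model contains time. A random effect for municipality or for the three groups does not remove a trend that all municipalities share. Followed literally, the plan would count such a trend as effect. Adding a period term after the data have been seen would be a post hoc choice.

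Fitting period also costs precision, and a calculation that omits it overstates the power available at a given number of children.

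The reason given for the ICC does not work either. The number of clusters does not determine an ICC. If the argument is that large units have low ICCs, no source is attached to 0.001. In either case three clusters is not the level at which the trial allocates and models: that is 16 municipalities.

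**Working it through.** **Inputs from the documents.** Difference 2, SD 5.7, ICC 0.001, alpha 0.05, 80% power, 306 required, 460 planned (780 × 0.85 × 0.70 = 464, given as 460), 16 municipalities in groups of 6, 5 and 5, four steps (0 to 3).

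**Assumptions.** Two-sided test, equal-sized municipalities and, at first, equal numbers per step and no covariates. The step calendar is in a figure and an appendix that were not available to me.

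**1. The plan's 306.** A two-group comparison needs 4 × (1.96 + 0.8416)² × 5.7² / 2² = 255.0, or 256 with whole numbers per arm. The design effect is 1 + (m − 1) × 0.001 for cluster size m. Reaching 306 needs a factor of about 1.20 (306/256 = 1.195), so m is about 195 to 200. The paragraph states no m, and sizes built from its own figures do not give 306: 460/3 = 153 gives 294, 780 × 0.85/3 = 221 gives 312, and 780/3 = 260 gives 321. A two-group formula with a clustering inflation can therefore produce 306, but the text does not say how it was obtained.

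**2. The stepped wedge.** The model has a fixed effect per step, an intervention effect and a municipality random intercept. Each of the 16 × 4 cells holds N/64 children. For municipality i, V_i has 5.7² × ICC in every entry, plus 5.7² × (1 − ICC)/(N/64) on the diagonal. The SE is the square root of the intervention entry of (Σ X_i′V_i⁻¹X_i)⁻¹, and power = Φ(2/SE − 1.96).

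| N | ICC | SE, period fitted | Power | SE, no period | Power |
|---|---|---|---|---|---|
| 306 | 0.001 | 0.975 | 53.6% | 0.653 | 86.5% |
| 460 | 0.001 | 0.797 | 70.9% | 0.533 | 96.4% |
| 306 | 0.05 (assumed) | 1.054 | 47.5% | 0.665 | 85.3% |
| 460 | 0.05 (assumed) | 0.880 | 62.2% | 0.547 | 95.5% |

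For example, at 460 and ICC 0.001: 2/0.797 − 1.96 = 0.55, and Φ(0.55) = 0.709. The detectable difference at 80% power, 2.80 × SE, is 2.23 points at 460 and 2.73 at 306 (ICC 0.001). Under these assumptions 80% power for 2 points needs 575 children.

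**3. Sensitivity, period fitted.**

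| Scenario | 306 | 460 |
|---|---|---|
| Steps 2:1:1:2, ICC 0.001 / 0.05 | 39% / 36% | 54% / 49% |
| Steps 1:2:2:1, ICC 0.001 / 0.05 | 66% / 56% | 82% / 70% |
| Steps 1:3:3:1, ICC 0.001 / 0.05 | 71% / 59% | 87% / 73% |
| Equal steps, ICC 0.001, covariate R² 0.20 (assumed) | 63% | 80% |
| Equal steps, ICC 0.001, plus group-level ICC 0.01 (assumed) | 46% | 60% |

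A heavier weight on the outer steps (3:1:1:3) lowers 460 to 43% at ICC 0.001. A t reference with 14 degrees of freedom lowers the equal-step 71% to about 65%.

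**4. Drift.** Suppose mean SDQ moves linearly by 1 point from Step 0 to Step 3 in every municipality, with equal steps. Without a period term the estimated effect shifts by 0.55 to 0.62 points for ICCs from 0.001 to 0.05. With period fitted the shift is zero. The size of the drift is hypothetical.

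**The case against.** The strongest reply is that nobody plans to analyse 306 children. The plan expects 460, half as many again, and intends covariates that the main table leaves out. An assumed R² of 0.20 with equal steps gives 80% at 460, and a favourable split does so without covariates. Combining R² 0.20 with a 1:3:3:1 split brings even 306 to about 80%. The ICC of 0.05 is also my assumption; only 0.001 is in the plan. All of this stands, and it rules out the stronger reading that the trial is underpowered at 460. It does not rescue the statement as written, because none of these features is shown to enter the calculation, and the margin of 460 over 306 is measured against a figure that ignores period.

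Three further inferences are not supported. One is that 306 is an arithmetic slip: a two-group formula can reach it, so the fault lies in the method. Another is that the result will be biased: no SDQ trend is reported. Section 3.1 says only that training to identify eligible children was intensified during recruitment, which could change case mix over time. The third is that 471 children will have a 24-month SDQ. The Protocol calls them available for follow-up and next gives 18-month participation of 90% and 83%. If 471 is a number before attrition, those rates would leave 471 × 0.83 = 391 to 471 × 0.90 = 424.

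Finally, recruitment was due to close on 31 October 2023, so restated power changes no enrolment. That is true, and it makes the model sentence the part that affects the result.

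**Conclusion.** The concern holds as a fault of method and model specification. I have high confidence that no period term appears in either the sample size text or the model text, and that the stated reason for the ICC does not support it.

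The power figures are illustrations and carry less confidence. At the plan's ICC of 0.001, with period fitted, equal steps and no covariates, power is about 54% at 306 and 71% at 460. With an assumed ICC of 0.05 it is 48% and 62%. Across splits from 2:1:1:2 at ICC 0.05 to 1:3:3:1 at ICC 0.001, power at 460 runs from about 49% to 87%. The documents therefore show that the 306/80% statement does not describe this design. They do not show that 460 is too few.

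**What to change.** Before the analysis:

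- State in section 4.2 that step (period) is a fixed effect in the primary SDQ model, and say whether the random effect for the three groups is kept.
- Replace the 306/80% statement and the three-clusters reason with the power, or the detectable difference at 80% power, for the actual number of children with a 24-month SDQ (planned 460). Compute it from the 16 municipalities, the actual step dates and cluster-period sizes, and a municipality-level ICC range such as 0.001 to 0.05. Include the group-level random effect if it is kept, and show any covariate gain as a stated R² assumption.
- Clarify whether the 471 in section 3.1 is before or after attrition.
- If 306 is kept for the record, label it as a calculation without period effects and give its method and cluster size.

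The cost is one sentence in the model description and one rewritten paragraph, with no extra enrolment. The stated power is likely to look less favourable and the confidence interval will be wider. At 460 with equal steps and ICC 0.001 the SE goes from about 0.53 to 0.80, so the 95% half-width goes from about 1.04 to 1.56 points.

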The outbreak of the COVID pandemic in the beginning of March 2020 has had an immense influence on the study-flow and the recruitment rate in the participating municipalities, which at times has ranged from 70% in some municipalities to zero in others. Consequently, we have had to extend the overall study period including the recruitment period, and strong efforts have been made to intensify the recruitment in the individual municipalities. The PUF-program education to correctly identify the vulnerable children, has thus been boosted, delivering regular brush-up courses by special educated project CHNs. A total of seven of these project CHNs have been allocated to the Infant Health Study, to further intensify the identification of children meeting the criteria of inclusion, and specifically, to intensify the support to the CHNs in municipalities having low rates of recruitment.

During 2021-2022, the recruitment aims have been adjusted. Firstly, the launch of the recruitment period has been postponed to August 16, 2021, and next, the period of recruitment has been extended to October 31, 2023. Based on the frequency of children identified with three or more vulnerabilities so far, we have adjusted the overall expected identification rate from 16 pct. to 10 pct. of the screened children, with some municipalities recruiting up to 70 % of what we expect, while others only recruit 30% or even less. Still, throughout the recruitment period we have realized a relatively high rate of participation among eligible children invited for participation.

Per October 2022, the recruitment aims are adjusted to comprise around 780 children at baseline, and around 460 children available for the follow-up at 24 months (see Figure 1).

For further sample size justification please see section 4.2.

Supplementary information October 2024

June 2024-october the data collection in project was forced to pause caused by discrepancies in the ethical evaluations completed by the Research Ethics Committee REC University of Southern

INFANT HEALTH

Denmark in 2020 and 2022, and the local Committees on Health Research Ethics in the Capital Region of Denmark June 2024. After approval of the project continuation in the remaining period of data collection from the local Committees on Health Research Ethics, research activities were re-up taken October 2024.

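### The 780 children called baseline are counted before the 85% participation step, the 80% power at 306 does not describe the stepped-wedge design, and the plan does not say what the 471 of October 2024 counts

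*Protocol*

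**What the plan says.** The sample-size text in section 4.2 is the same in the Protocol and in the Combined protocol and SAP. It sets out "to detect a difference in the SDQ total score of 2 while assuming a standard deviation of 5.7", with a small cluster effect ("assuming an intraclass correlation of 0.001 as there are only 3 large clusters involved"), "a significance level of 0.05 and with 80% power", and concludes "we need a total sample size of 306 participants". Children per cluster, allocation ratio and sidedness are not given. The section then expects 85% participation at baseline and 30% dropout by 24 months, "leaving a total of 460 children available for assessments of the primary outcomes, conditioned a recruitment of about 780 children at baseline".

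The October 2022 status in section 3.1 repeats the label: "the recruitment aims are adjusted to comprise around 780 children at baseline", with about 460 for the 24-month follow-up.

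The October 2024 supplement to section 3.1 appears in the Protocol only. It reads "Per October 2024, the around 471 children available for the follow-up" and gives 18-month participation of 90% in controls and 83% in cases. It does not state the follow-up age, or whether 471 counts children enrolled, still in follow-up, or with data. Section 4.2 was not revised when this was added.

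Section 3.2 describes a stepped wedge of 16 municipalities in three groups (6+5+5), with all municipalities as controls at step 0 and control families recruited in the early phases. The models in section 4.2 have municipality and cluster random effects. No period term is named.

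**The concern.** A reader uses these figures to judge how many children the primary SDQ analysis will have and what difference it could detect. Three things stand in the way. The starting number is labelled as though participation had already been applied, yet the end number applies it again. The 80% power belongs to a parallel comparison, although intervention and calendar time run together in this design. The latest status figure cannot be placed in the chain from enrolment to 24-month outcome. If section 4.2 stands as written, a null SDQ result would be read as coming from a better-powered trial than the design provides.

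**Working it through.** **1. Enrolment chain (inputs from section 4.2).**
- 780 × 0.85 × (1 − 0.30) = 464, which matches the stated 460.
- On that reading, enrolled children number 780 × 0.85 = 663.
- If 780 children were truly at baseline: 780 × 0.70 = 546.
- The two readings differ by 546 − 464 = 82 analysable children.

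**2. The 306 (difference 2, SD 5.7; two-sided 0.05 and 1:1 allocation assumed).**
- Unadjusted n per arm = 2 × (5.7 × (1.960 + 0.842) / 2)² = 127.5, so 128; the t-based version is 129.
- Design effect = 1 + (m − 1) × 0.001, where m is the number of children per cluster.

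| m | Where m could come from | Normal-based total | t-based total |
|---|---|---|---|
| 102 | 306 / 3 | 282 | 286 |
| 153 | 460 / 3 | 296 | 298 |
| 182 | 546 / 3 | 304 | 306 |
| 195 | 780 / 4 | 306 | 310 |
| 260 | 780 / 3 | 324 | 326 |

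Without rounding per arm, the normal version gives 255.0 × 1.200 = 306 at m = 201. So 306 is reachable at m of about 182–201. The documents do not say which m was used.

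**3. Power under the stepped wedge.** Assumptions: step 0 plus three steps, taken as four equal periods; groups of 6, 5 and 5 municipalities switching at steps 1, 2 and 3; equal cell sizes N/64; a municipality random intercept; fixed period effects; no covariate gain. The ICC values 0.01 and 0.05 are assumptions placed beside the plan's 0.001.
- For each municipality's four period means, V = ICC × 5.7² × J + (1 − ICC) × 5.7² / (N/64) × I.
- The variance of the effect is the treatment element of (Σ X′V⁻¹X)⁻¹.
- Power = Φ(2/SE − 1.96); detectable difference at 80% power = 2.80 × SE.

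| N | SE at ICC 0.001 / 0.01 / 0.05 | Power (%) | Detectable difference (points) |
|---|---|---|---|
| 306 | 0.975 / 0.999 / 1.054 | 54 / 52 / 48 | 2.73 / 2.80 / 2.95 |
| 330 | 0.939 / 0.964 / 1.019 | 57 / 55 / 50 | 2.63 / 2.70 / 2.85 |
| 460 | 0.797 / 0.825 / 0.880 | 71 / 68 / 62 | 2.23 / 2.31 / 2.47 |
| 471 | 0.788 / 0.816 / 0.871 | 72 / 69 / 63 | 2.21 / 2.29 / 2.44 |

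Under the same assumptions, 80% power needs about 575 / 631 / 739 children. The loss does not come from imbalance: 6×3 + 5×2 + 5×1 = 33 of the 64 municipality-periods are intervention. Dropping the period effects from the model returns power at 306 to about 85–87%, so the loss is the price of adjusting for calendar time.

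**4. The 471.** Recruitment at 9–10 months of age ran to 31 October 2023. The last recruits reach 24 months 14–15 months later, around the turn of 2024 to 2025, which agrees with the January 2025 end of data collection in section 6. At the end of October 2024 they were 21–22 months old. Data collection was also paused from June to October 2024. So 471 cannot consist wholly of children with completed 24-month assessments.
- If 471 precedes all attrition: 471 × 0.70 = 330 at the planned dropout; 471 × 0.83 = 391 and 471 × 0.90 = 424 at the 18-month participation rates.
- If 471 is already net of loss: about 471.

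**The case against.** The best defence is that the plan meets its own requirement on every reading. The 460 exceeds 306 by half, and even 330 exceeds it. On the plan's two-sample method with a design effect of 1.194, power is 83% at 330, 93% at 460 and 94% at 471. That is correct, and it means no shortfall follows from the status figures on that method. Reading 780 as truly enrolled would also be more favourable (546), so the label hides no deficit.

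A reader might infer that 306 is a miscalculation, because clusters of 102 or 153 do not return exactly 306. The documents do not support this. Cluster size is unstated, and sizes of about 182–201 reproduce the figure. Nor does 460 depend on 306; it comes only from 780 and the two rates.

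A reader might also infer that 471 is an enrolled count, so that the analysable number is 330 to about 400. The dates show only that 24-month follow-up was incomplete. The October 2022 status uses nearly the same phrase for the post-dropout 460, so 471 may be its achieved counterpart. In that case, applying 30% dropout would count losses twice. The 18-month rates do not bound 24-month response, since a family that missed 18 months may still answer later.

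The stepped-wedge power is also open to challenge: equal municipalities and periods are a simplification when section 3.1 reports very uneven recruitment, and section 4.2 plans prognostic covariates, including baseline ASQ:SE2. This stands in part. If covariates explained 25% of the variance (an illustrative assumption), 471 children would act like 471 / 0.75 = 628, against the 575 / 631 / 739 needed: enough at ICC 0.001, borderline at 0.01, too few at 0.05. At 330 the equivalent is 440, too few throughout. The plan makes no such claim for its covariates.

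**Conclusion.** The point holds in three limited parts.
- **The 780 is mislabelled.** This follows from the plan's own rates and needs no assumption. About 663 children would be enrolled on the chain that yields 460.
- **The 80% power at 306 does not carry over to this design once calendar time is adjusted for.** Under the stated assumptions it is about half (54/52/48%), and 80% is not reached at 460 or 471 without a covariate gain. This rests on fitting period effects, which section 4.2 does not name. Leaving them out would restore the nominal power only by letting any time trend enter the intervention effect, since controls are recruited early.
- **The 471 is undefined.** The analysable number could be about 330, 391–424, or near 471. The documents do not settle which.

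An arithmetic error in 306, an established drop to about 330, and a miss of the plan's own 306 are not supported.

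**What to change.** In section 4.2 and the October 2022 status in section 3.1, restate the chain as about 780 invited, 663 enrolled and 464 at 24 months. Give the cluster size, allocation and sidedness behind 306; do not replace 306 with a figure built on a guessed cluster size. In the October 2024 supplement, say what 471 counts, and add the number enrolled and the number with a 24-month SDQ, each by group. Replace the 80% at 306 with the power or detectable difference from a period-adjusted stepped-wedge model at the actual number, over a stated ICC range and with any covariate gain made explicit. Carry the same text into the Combined protocol and SAP.

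The cost is a change of wording, a short calculation and less favourable stated figures. No extra enrolment is involved.
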